#### IRBs/IECs

A copy of this amended protocol will be sent to the Institutional Review Board (IRBs)/Independent Ethics Committee (IECs) and Health Authorities.

The changes described in this amended protocol require IRB/IEC and Health Authority approval according to local regulation prior to implementation. In addition, the changes herein will affect the Informed Consent, sites are required to update and submit for approval a revised Informed Consent that takes into account the changes described in this amended protocol.

# **Protocol summary**

Protocol number	CQBW251C12201
Full Title	A randomized, subject- and investigator-blinded, placebo-controlled, parallel group study to assess the safety, tolerability, pharmacokinetics and pharmacodynamics of QBW251 in subjects with bronchiectasis
Brief title	Study of safety, tolerability, pharmacokinetics and pharmacodynamics of QBW251 in subjects with bronchiectasis
Sponsor and Clinical Phase	Novartis Phase II
Investigation type	Drug
Study type	Interventional
Purpose and rationale	The purpose of this study is to determine whether potentiating the cystic fibrosis transmembrane conductance regulator (CFTR) with QBW251 in patients with bronchiectasis will demonstrate clinical safety and efficacy related to improved mucociliary clearance with reduced bacterial colonization as potential drivers of airway obstruction, reduced airway inflammation, exacerbations and mucus load, improved lung function, clinical symptoms and quality of life to support further development in bronchiectasis.
Primary Objective(s)	The primary objective for this study is to determine the efficacy of QBW251 compared to placebo with respect to change from baseline in bacterial load of colony forming units (CFU/mL, 1 CFU/mL = 1 CFU/g) of potentially pathogenic microorganisms in spontaneous sputum at week 12.
Secondary Objectives	Objective 1: to assess the change on sputum bacterial clearance of QBW251 compared to placebo with respect to proportion of patients with absence of any CFU of potentially pathogenic bacteria in sputum culture after 12 weeks of treatment.
	Objective 2: to assess the change on patient reported outcomes on bronchiectasis symptom assessment of QBW251 compared to placebo with respect to change from baseline in Quality of Life Questionnaire for Bronchiectasis (QOL-B) after 12 weeks of treatment.
	Objective 3: to assess the change of fibrinogen plasma concentration of QBW251 compared to placebo after 12 weeks of treatment.
	Objective 4: to assess the change in rescue medication use of QBW251 compared to placebo after 12 weeks of treatment.
	Objective 5: to assess the effect of QBW251 after 12 weeks of treatment, on the change from baseline in lung function from measurement by spirometry of pre-bronchodilator FEV1 and FVC.
	Objective 6: to assess the effect of QBW251, after 12 weeks of treatment, on the change from baseline in airway structure and function from measurements by HRCT of airway wall, lumen parameters and the extent of global and regional air trapping.
	Objective 7: to assess the pharmacokinetic profile of QBW251 in subjects by measurement of concentrations of QBW251 in plasma and calculation of relevant PK parameters including Cmax, AUC on Days 1 and 28 (for a subset of patients at selected sites). Pre- and post- dose concentration (Ctrough and around Cmax) on Days 1, 28, 56 and 84 (for all patients).

Objective 8: to assess the safety and tolerability of QBW251 by reporting the occurrence of adverse events, vital signs, ECG and safety laboratory changes during the study

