#### Screening visit (Day -42 to Day -1):

Screening assessments can be performed over a 6-week period maximum (up to 42 days).

Informed consent must be obtained prior to implementing any study specific procedure. Inclusion and exclusion criteria will be checked to confirm patient's eligibility.

Sputum will be collected once within the screening window to confirm bacterial load with at least one strain of potentially pathogenic bacteria (refer to Section 5.1). The sputum microbiology results at screening will need to be available prior to randomization. Retesting is allowed once.

At screening, all subjects will be provided with an electronic diary (eDiary) and be trained on its use on how to record information about their rescue medication (salbutamol/albuterol), other concomitant medication use, how to complete questionnaires, how to record study medication intake (from Day 1 onwards) as well as symptoms.

A HRCT assessment will be performed during screening period except at selected sites where HRCT is optional with Sponsor approval.

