# 2 Objectives and endpoints

Table 2-1 Objectives and related endpoints

Objective(s)	Endpoint(s)	
Primary objective(s)	Endpoint(s) for primary objective(s)	
To assess the change on sputum bacterial colonization	• Change from baseline in bacterial load of colony forming units (CFU/mL, 1 CFU/mL = 1 CFU/g) of potentially pathogenic microorganisms in spontaneous sputum with QBW251 compared to placebo at week 12	
Secondary objective(s)	Endpoint(s) for secondary objective(s)	
• To assess the change of QBW251 compared to placebo on sputum bacterial clearance	• Proportion of subjects with absence of any CFU of potentially pathogenic bacteria in sputum culture after 12 weeks of treatment	

Ok	ojective(s)	Endpoint(s)	
•	To assess the change on patient reported outcomes on bronchiectasis symptom assessment	
 
Changes from baseline in Quality of Life Questionnaire for Bronchiectasis (QOL-B) (Respiratory symptoms domain) after 12 weeks of treatment.
 
	
•	To assess the change of fibrinogen plasma concentration	
 
Change from baseline in fibrinogen plasma concentration after 12 weeks of treatment
 
	
•	To assess the change in rescue medication use	• Change from baseline in rescue medication use (salbutamol/albuterol) after 12 weeks of treatment.	
•	To assess the change on lung function.	• Changes from baseline in pre- bronchodilator FEV1, FVC after 12 weeks treatment, measured by spirometry	
•	To assess the change in airway structure and function	• Change from baseline in airway wall and lumen parameters along with extent of global and regional air trapping after 12 weeks of treatment, as measured by HRCT.	
•	To assess the pharmacokinetics of QBW251 in patients with bronchiectasis	• Assessment of drug exposure (Cmax, AUC) and other PK parameters when feasible on Days 1 and 28 (for a subset of patients at selected sites).  Pre- and post- dose concentration (Ctrough and around Cmax) on Days 1, 28, 56 and 84 (for all patients).	
•	To assess the safety and tolerability of QBW251 in patients with bronchiectasis	All safety endpoints (including adverse events, vital signs, ECG, and safety laboratory changes) during the study	
Exploratory objective(s)		Endpoint(s) for exploratory objective(s)	

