# Screening visit (Day -42 to Day -1):

Screening assessments can be performed over a 6-week period maximum (up to 42 days).

Informed consent must be obtained prior to implementing any study specific procedure. Inclusion and exclusion criteria will be checked to confirm patient's eligibility.

This check includes medical history, maintenance therapy of LABA/ICS or LABA/LAMA or LABA/LAMA/ICS and/ or macrolides, physical examination, ECG, vital signs, oxygen saturation, and clinical laboratory evaluations (hematology, blood chemistry, coagulation, urinalysis). Sputum will be collected once within the screening window to confirm bacterial

load with at least one strain of potentially pathogenic bacteria (refer to Section 5.1). The sputum microbiology results at screening will need to be available prior to randomization. Retesting is allowed once.

At screening, all subjects will be provided with an electronic diary (eDiary) and be trained on its use on how to record information about their rescue medication (salbutamol/albuterol), other concomitant medication use, how to complete questionnaires, how to record study medication intake (from Day 1 onwards) as well as symptoms.

A HRCT assessment will be performed during screening period except at selected sites where HRCT is optional with Sponsor approval. The screening HRCT can also be used to confirm the diagnosis of BE if no historical HRCT is available. At selected sites, where HRCT is optional, diagnosis of BE must be available from a historical scan.

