## **Baseline/Randomization Day 1:**

Subjects who meet the eligibility criteria will be admitted to baseline/Day1 safety and efficacy evaluations before randomization.

During baseline, sputum samples will be collected at the same time of the day (sputum collection procedure and timing will be detailed in the SOM and laboratory manual) for biomarker assessments (bacterial load and colonization as well as inflammatory markers). Subjects will be also asked to complete various scales and questionnaires (refer to the Assessment Schedule for the type of questionnaires and time points).

There is no antibiotic intervention or change of mucous clearance regimen allowed for pulmonary exacerbation between screening and baseline except for the use of macrolides for subjects who are on this medication before enrolment. In this case, macrolides are to be continued at the same dose and regimen during the study. Baseline mucous regimen should remain unchanged between screening and baseline.

Once all baseline assessments have been completed and subjects are again confirmed as being eligible for the study, they can be randomized on the same day (baseline/randomization Day 1). In the case that sputum sample cannot be collected or other assessments can't be completed at baseline visit for various reasons, the site must not randomize the subject on the same day. An unscheduled visit needs to be planned for sputum collection prior to randomization and treatment allocation. Once sputum is collected and required assessments are completed, the subject can be randomized on the same day of the unscheduled visit.

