### 5.1 Inclusion criteria

Subjects eligible for inclusion in this study must meet all the following criteria:

- 1. Written informed consent must be obtained before any assessment is performed.
- 2. Male or female patients aged  $\geq 18$  years at screening.
- 3. Proven diagnosis of bronchiectasis by chest CT at screening as determined by the investigator. The screening HRCT can be used to confirm the diagnosis if no historical chest CT is available.
- 4. Evidence of sputum bacterial load of ≥10^6 CFU/mL with at least one potentially pathogenic microorganism at screening (*H. Influenzae*, *M catarrhalis*, *S aureus*, *S pneumoniae*, *Enterobacteriaceae*, *P aeruginosa*, *Stenotrophomonous maltophilia*, or any potential pathogenic non-fermenting Gram-negative bacteria measured by dilution/outgrowth.) NOTE: *H. parainfluenzae* is not considered pathogenic in this study and therefore growth of this organism alone does not satisfy this criterion.
- 5. Documented history of at least one bronchiectasis exacerbation between January 2019 to study screening.
- 6. Patients with bronchial hypersecretion, defined as productive cough that occurs on most days (defined as >50% days) for at least three consecutive months within 12 months prior to screening, as assessed by documentation of patient recollection (anamnesis) or documented in patients' record.
- 7. Patients are allowed to stay on fixed or free combinations of LABA/LAMA or LABA/ICS or LABA/LAMA/ICS as maintenance therapy if they are treated with them at a stable dose for the last 3 months prior to screening. Patients are also allowed to stay on macrolides as maintenance therapy if they are treated with them at a stable dose 3 months before screening. Patients will be allowed to use mucolytics or hyperosmolar agents if they were treated with them before study start.

- If prescribed, patients are included in the study with unchanged chest physiotherapy for at least 4 weeks prior to screening.
- 8. Clinically stable pulmonary status in the opinion of the investigator and unlikely to require any change in the standard regimen of care during the course of the study.

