# 12.5 Analysis of secondary endpoints

# 12.5.1 Efficacy and/or Pharmacodynamic endpoint(s)

# 12.5.1.1 Proportion of patients with absence of any CFU or CFU counts below the limit of quantification

The proportion of patients with absence of any CFU or CFU counts below the limit of quantification at week 12 will be analyzed using a logistic regression. The model will include treatment, baseline macrolide use as fixed class effects and the number of bronchiectasis exacerbations in the 12 months prior to screening as a categorical variable. The estimated odds ratios will be displayed along with the associated 80% confidence intervals.

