		, , , , , , , , , , , , , , , , , , ,	Often	2
			Sometimes	3
			Never	4
37	BQOL137	Woken Up Due to Coughing	Always	1
			Often	2
			Sometimes	3
			Never	4
37	BQOL137	Woken Up Due to Coughing	Always	1
			Often	2
			Sometimes	3
			Never	4

Proportion of subjects with absence of any CFU of potentially pathogenic bacteria in sputum culture.

The number and percentage for participants with no CFU in sputum will be tabulated by treatment arm and visit. Percentages will be based on the number of participants for whom microbiology results exist per visit.

Change from baseline in rescue medication use (salbutamol/albuterol)

Baseline rescue medication use is defined as the average number of puffs per day in the screening period and the morning record at Day 1. All days with data will be used for calculating the baseline value.

The total number of puffs of rescue medication will be divided by the total number of (full or half) days with non-missing rescue data to derive the mean daily number of puffs of rescue medication taken for the patient for each given visit interval. If the number of puffs is missing for part of the day (either morning or evening) then a half day will be used in the denominator. No imputation will be used for missing rescue therapy. Any values >48 for the number of puffs of rescue medication in a 12 hour period will be set to missing. These high numbers are not realistic and could impact the analysis.

If a participant has only 0 to 6 days of data recorded, the baseline will be set to missing. Participants must have at least 7 days of rescue medication data recorded to have a baseline level calculated

The post-baseline treatment period is defined as the period from the evening record of Day 1 up to the morning assessment following the day of the last dose of double-blind treatment. Missing diary data will not be imputed. For the derivations of on-treatment mean weekly and mean monthly number of puffs, only values from Day 1 up to the date of last dose of double-blind treatment will be considered.

The daily number of puffs will be averaged for each week (Week1, Week2, etc). A patient needs to have at least 4 days of data in any week in order for the mean score to be calculated.

Monthly means over a 4-week period will also be calculated. A patient needs to have at least 3 weekly means in that month in order for the monthly mean to be calculated. Mean daily number of puffs will be summarized descriptively by monthly interval.

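### The secondary clearance endpoint does not separate clearance on treatment from cultures that were already negative on Day 1

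*Protocol*

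**What the plan says.** - **Endpoint.** The Protocol summary (Secondary Objectives, Objective 1) assesses clearance by the "proportion of patients with absence of any CFU of potentially pathogenic bacteria in sputum culture after 12 weeks of treatment", and Protocol Table 2-1 gives the same endpoint. Neither document restricts this to patients with a positive Day 1 culture.
- **Entry.** Inclusion criterion 4 (Protocol 5.1) asks for a load of at least 10^6 CFU/mL "with at least one potentially pathogenic microorganism at screening". Screening may last up to 42 days. Protocol 3.1 states: "The sputum microbiology results at screening will need to be available prior to randomization". For Day 1 it requires that a sputum sample be collected, sets no condition on the result, and allows randomisation on the same day.
- **Baseline.** SAP 6.1.2 takes baseline CFU from the baseline sample and recognises no growth as a possible result at a visit.
- **Analysis set.** The PD set needs baseline data to be available, not positive (Protocol 12.1, SAP 4).
- **Analysis.** Protocol 12.5.1.1 plans a logistic regression: "The model will include treatment, baseline macrolide use as fixed class effects", plus prior exacerbations. It has no baseline CFU term. SAP 6.2.1 drops the secondary models because the study was terminated and tabulates counts and percentages by arm and visit: "Percentages will be based on the number of participants for whom microbiology results exist per visit".
- **Randomisation.** The strata are macrolide use and region (Protocol 6.3.2), not bacterial load.

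**The concern.** Clearance names a transition from a positive culture to a negative one. The primary endpoint and the other secondary efficacy endpoints are changes from baseline, and the trial's baseline is Day 1. A culture that turned negative between screening and the first dose cannot reflect study drug, yet the planned percentage counts it in the same way as a conversion on treatment.

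The by-visit table is now the only planned analysis of this endpoint. It is marginal: even with a baseline row, it cannot show whether the patients negative at week 12 are the ones who were negative on Day 1. At stake is whether the reported figure answers the stated objective. No trial decision depends on it.

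**Working it through.** **No plan figure for this endpoint.** The documents give no expected rate, power or sample size for clearance. The one number borrowed below is the SD of 2.8 log10 from Protocol 12.8.1. That section's power can be reproduced: with 30 completers per arm and a difference of 1.5, 1.5 / (2.8 × √(2/30)) = 2.07, and Φ(2.07 − 1.28) = 78.6%, against the stated 79% (one-sided 10%). This confirms how the SD is used there. It says nothing about clearance.

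**Notation.** q is the share negative on Day 1, s the probability that such a patient is negative at week 12, and c the probability that a patient positive on Day 1 is negative at week 12. None of the three is in the documents.

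- Expected week-12 percentage: q·s + (1 − q)·c.
- Expected shift in the arm difference from k excess Day 1 negatives in an arm of n: (k/n)·(s − c).
- Share of week-12 negatives already negative on Day 1: q·s / [q·s + (1 − q)·c].

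**Size of q.** Assumptions: patient mean load normal around 6 or 7 log10, between-patient SD 1 to 2, within-patient SD 2.8/√2 = 1.98, entry on a screening value of at least 6 with one retest, and no treatment effect.

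| Assumed culture limit | q |
|---|---|
| 10^1 | 0.3–1.0% |
| 10^2 | 1.0–2.8% |
| 10^3 | 3.0–6.8% |

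Two retests raise the top to 7.5%. (Protocol 8.1 allows two repeats of the screening load, while 3.1 and 8.3.1 allow one; these sections need to be reconciled.) A simpler bound, Φ((limit − mean)/SD), with means of 6 to 8 and limits of 10^1 to 10^2, gives 0 to 2.3% if the screening-to-baseline SD is 1 to 2 logs, and 0.6 to 7.7% if it is 2.8.

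**Imbalance at q = 0.3% to 7%** (two independent binomials, 30 per arm). The expected number is 0.1 to 2.1 per arm. The chance that the arms differ by at least one is 16% to 79%; by at least two, 1% to 44%.

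**How much passes through.** In the same model s is 1% to 20% and s − c is 0.01 to 0.15. One excess Day 1 negative in 30 then shifts the expected difference by 3.3 × (0.01 to 0.15) = 0.03 to 0.5 points. With an assumed 12 per arm after termination it is 8.3 × (0.01 to 0.15) = 0.1 to 1.2 points.

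If negative cultures are more persistent than this model allows, the effect is larger. With c = 10% and s from 0.3 to 1.0, one excess patient in 30 shifts the difference by 0.7 to 3.0 points, and three by 2.0 to 9.0.

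**Share of reported clearances already negative on Day 1.** In the model this is 1% to 20%. With the more persistent assumption (q = 5%, s = 0.7, c = 10%) it is 0.035 / (0.035 + 0.095) = 27%.

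**Type I error.** A simulated unadjusted one-sided 10% z-test with 30 per arm, s = 0.7 and c = 10% rejects 10.9% of the time at q = 0 and 10.7% at q = 10% or 20%. Day 1 negatives do not inflate it.

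**The case against.** A reader might infer that the endpoint does not measure clearance at all. The documents do not support that. Criterion 4 means that every eligible patient had a heavily positive culture at screening, so no CFU at week 12 is a conversion relative to screening. What the endpoint fails to do is place that conversion after the first dose.

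A reader might also infer that a Day 1 imbalance goes straight into the week-12 percentages. That would need every Day 1 negative to stay negative and no positive patient to convert. The factor is s − c, which is small in the model above.

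Several provisions also make a fall from 10^6 to no growth less likely. Non-macrolide antibiotics in the 4 weeks before Day 1 are an exclusion (criterion 24), an exacerbation between screening and baseline prevents enrolment (criterion 12), and a suboptimal sputum sample triggers a request for a new one (Protocol 8.3.1). The SD of 2.8 refers to change to Day 84 and was chosen conservatively, so using it for a gap of at most 42 days probably overstates q.

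Finally, SAP 6.1.3.2 displays individual bacterial loads, the primary analysis of the same cultures adjusts for baseline, and the clearance table carries no test or decision.

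All of this stands, and it makes the point minor. It does not remove it: none of these provisions requires a positive Day 1 culture, and neither the by-visit table nor the individual display changes the percentage reported as clearance.

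**Conclusion.** The point holds in a limited form. As defined, the endpoint cannot separate clearance on treatment from conversion before the first dose, because a patient negative on Day 1 and at week 12 is counted as cleared and nothing adjusts for Day 1 status.

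Probably few patients are affected: about 0.3% to 7%, resting on an assumed mean load, an assumed culture limit and a borrowed SD. An arm imbalance passes into the week-12 figures by P(stay negative) minus P(conversion). It is chance noise, without systematic bias or type I error inflation. If no patient is negative on Day 1, the reported figure is unchanged. The importance is minor: a descriptive percentage in a terminated, non-confirmatory study should match the objective that it is reported under.

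**What to change.** In SAP 6.2.1 and Protocol 12.5.1.1:

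1. Report clearance as no CFU at the visit among PD-set patients whose Day 1 culture grew at least one potentially pathogenic organism, with those patients who have a result at the visit as the denominator.
2. Show the number negative on Day 1 per arm, or give a baseline-by-week-12 shift table by arm.
3. Keep the current all-patient percentage as a second row.

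Protocol 12.5.1.1 also counts values below the limit of quantification as absence, whereas Table 2-1 and the SAP do not. The new sentence should use one definition of negative at both time points.

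The cost is one sentence and one filter on data already collected. Day 1 status is fixed before treatment, so the restriction does not break the randomised comparison. The denominator becomes slightly smaller: at q = 5%, about 28 or 29 of 30 patients per arm remain.

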#### 12.5.1.2 Change from baseline in fibrinogen plasma concentration

The change from baseline in fibrinogen is assumed normally distributed. An MMRM will be fitted to the changes from baseline in fibrinogen for all time points until Day 84 visit including the following fixed factors: treatment group, visit, treatment group by visit interaction, baseline macrolide use, and baseline fibrinogen value by time interaction.

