# 12.5.1.5 Change from baseline in airway wall and lumen parameters along with extent of global and region air trapping as measured by HRCT

Change from baseline in airway wall and lumen parameters will be analyzed using the same model as for the efficacy endpoint in Section 12.5.1.2. Global and region air trapping changes will be summarized. Contrasts for treatment differences will be provided together with two-sided 80% confidence intervals.

Any correlations between changes in air trapping and the lung function parameters measured by spirometry would be explored.

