#### 12.5.5 Patient reported outcomes

Quality of Life Questionnaire for Bronchiectasis (Respiratory symptoms) will be summarized by treatment groups and visit.

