6.2.2 Descriptive analyses

Summary statistics of change from baseline for each secondary efficacy endpoint will be provided by treatment group and visit for all secondary endpoints, if data allows.

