6.2.1 Statistical model, assumptions and hypotheses

The modeling for secondary pharmacodynamics objectives planned as per protocol will not be performed due to the study termination.

The secondary objective analysis will include all available data from subjects in the PD analysis set

Baseline secondary efficacy parameters (QOL-B, fibrinogen, FEV1, FVC) is defined as the measurement taken prior to the first dose of study drug (Day 1). If this assessment is missing (or is not confirmed to be pre-dose), then the screening assessment will be considered as baseline.

For spirometry data, only "acceptable" spirometry data will be included for analysis. In case 2 pre-dose spirometry assessments at -45min and -15min are performed, the first attempt (-45min) will be used for analysis if it's acceptable; if the first attempt is not acceptable, then the second attempt (-15min) will be used; if the second attempt is also not acceptable, then there would be no data available for that timepoint.

Changes from baseline in the Quality of life Questionnaire for Bronchiectasis (QOL-B) (Respiratory symptoms domain)

For Quality of Life Questionnaire for Bronchiectasis (QOL-B), the summary statistics for change from baseline in Respiratory Symptoms scale will be reported by treatment group and visit. The Respiratory Symptoms scale scores, with higher scores representing fewer symptoms or better functioning. Refer to Table 6-1 for details of response value and the corresponding scores for QOL-B Questionnaire (Respiratory symptoms domain) during reporting.

Table 6-1 Scoring algorithm for QOL-B Questionnaire (Respiratory symptoms domain)

QUESTION NUMBER	QUESTION SHORT NAME	QUESTION NAME	OPTIONS(CHAR)	OPTIONS(NUMERIC)
29	BQOL129	Congestion in Chest	A lot	1
			A moderate amount	2
			A little	3
			None at all	4
30	BQOL130	Coughing During Day Time	A lot	1
			A moderate amount	2
			A little	3
			None at all	4

31	BQOL131	Cough Up Sputum	A lot	1
		•	A moderate amount	2
			A little	3
			None at all	4
32	BQOL132	Sputum Observation	Clear	5
			Clear to yellow	4
			Yellowish-green	3
			Brownish-dark	2
			Green with traces of blood	
			Don't know	1
33	BQOL133	Shortness Breath	Always	0
33	BQOE133	When Active		1
			Often	2
			Sometimes	3
			Never	4
34	BQOL134	Have You Had Wheezing	Always	1
			Often	2
			Sometimes	3
			Never	4
35	BQOL135	Have You Had Chest Pain?	Always	1
			Often	2
			Sometimes	3
			Never	4
36	BQOL136	Shortness of Breath When Walking	Always	1

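### After termination the SAP drops every secondary efficacy model the protocol planned, so no secondary efficacy endpoint gets a treatment difference or interval, though the primary endpoint keeps both.

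*Protocol*

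**What the plan says.** **Objectives.** In the Protocol summary, Objectives 1 to 4 (clearance, QOL-B, fibrinogen, rescue use) name placebo as the comparator; the fibrinogen one reads "Objective 3: to assess the change of fibrinogen plasma concentration of QBW251 compared to placebo after 12 weeks of treatment". Objectives 5 and 6 (spirometry, HRCT) do not. Objective 5 begins "Objective 5: to assess the effect of QBW251 after 12 weeks of treatment, on the change from baseline in lung function". The objectives tables (Protocol Table 2-1, SAP Table 1-1) name placebo for only one secondary objective, sputum clearance.

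**Protocol analyses.**
- Clearance (12.5.1.1): logistic regression. "The estimated odds ratios will be displayed along with the associated 80% confidence intervals".
- Fibrinogen (12.5.1.2): "An MMRM will be fitted to the changes from baseline in fibrinogen for all time points until Day 84 visit".
- Rescue use (12.5.1.3) and FEV1/FVC (12.5.1.4): a similar MMRM.
- HRCT airway wall and lumen parameters (12.5.1.5): the same model. "Contrasts for treatment differences will be provided together with two-sided 80% confidence intervals".
- QOL-B (12.5.5): no model. "Quality of Life Questionnaire for Bronchiectasis (Respiratory symptoms) will be summarized by treatment groups and visit".

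**SAP.** Section 6.2, under the statistical model heading, states: "The modeling for secondary pharmacodynamics objectives planned as per protocol will not be performed due to the study termination". Under 6.2.2 Descriptive analyses it states: "Summary statistics of change from baseline for each secondary efficacy endpoint will be provided by treatment group and visit", with the caveat that the data must allow it. Clearance becomes a count and percentage by arm and visit, rescue use a monthly descriptive summary, and HRCT summary statistics with listings of air trapping. For the primary endpoint, SAP 6.1.3 replaces the Bayesian model with an MMRM adjusted for baseline and macrolide use, and promises treatment contrasts with two-sided 80% intervals.

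**The concern.** A placebo-controlled randomised trial measures a drug effect by the difference between arms. Two columns of change-from-baseline summaries do not state that difference, its uncertainty, or what it becomes after allowing for chance imbalance at baseline. Such imbalance is typically largest in a small, terminated sample.

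The stated reason is termination, yet the same SAP fits a between-arm model to CFU. Fibrinogen, spirometry and QOL-B are scheduled at the same post-baseline visits as CFU. Termination by itself therefore does not explain why CFU gets a contrast and the endpoints with a planned MMRM get none. At stake is how the secondary results are read: a gap between two arm means may be taken as a signal, or its absence as lack of effect, with no interval to show how little the data can say.

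**Working it through.** **1. The plan's own figure.** The only precision figure is for the primary endpoint (Protocol 12.8.1): about 79% power with 60 completers, difference 1.5, SD 2.8, 10% level.
- Standard error = 2.8 × √(2/30) = 0.723, and 1.5 / 0.723 = 2.075.
- One-sided 10%: power = Φ(2.075 − 1.282) = 0.786, which reproduces the stated figure. Two-sided 10% gives 0.666, which does not.
- Randomised number = 60 / (1 − 0.16) = 71.4, so 72, as stated.

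No precision figure is given for any secondary endpoint.

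**2. Endpoint by endpoint.**

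| Secondary efficacy endpoint | Protocol model | Between-arm estimate in SAP 6.2 |
|---|---|---|
| Sputum clearance | Logistic regression, 80% CI | None |
| QOL-B respiratory | None (summary only) | None |
| Fibrinogen | MMRM | None |
| Rescue use | MMRM | None |
| FEV1/FVC | MMRM | None |
| HRCT airway parameters | Same model, 80% CI | None |

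The protocol modelled 5 of 6; the SAP estimates a difference for 0 of 6. For air trapping, 12.5.1.5 says only that changes will be summarised, although its next sentence promises contrasts.

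**3. Would the CFU model carry over?** In Protocol Table 8-1, sputum load, coagulation (which includes fibrinogen), spirometry and QOL-B all have post-baseline assessments on Days 28, 56 and 84. SAP 6.2 still defines a baseline for fibrinogen, FEV1, FVC and QOL-B. The structure matches. HRCT has one post-baseline scan (Day 84), so a repeated-measures model reduces to an analysis of covariance.

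The SAP 6.1.3 model with three post-baseline visits has 6 treatment-by-visit means, 3 baseline slopes, 1 macrolide term and 6 covariance parameters: 6 + 3 + 1 + 6 = 16. With 5 patients per arm there are at most 10 × 3 = 30 observations. Convergence cannot be taken for granted, so a fallback is needed.

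**4. Uncertainty the tables would leave unstated.** For a simple difference in mean change, the 80% half-width in SD units is t(0.90, 2n−2) × √(2/n). The n values are assumptions, except 30, the planned completers per arm.

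| n per arm | Half-width (SD) |
|---|---|
| 5 | 0.88 |
| 7 | 0.72 |
| 10 | 0.59 |
| 15 | 0.48 |
| 20 | 0.41 |
| 30 | 0.33 |

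With no true difference, the observed gap would exceed these values in one trial in five.

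**5. Value of baseline adjustment.** With equal baseline and follow-up variances and baseline-to-week-12 correlation ρ, adjustment multiplies the variance of the difference, relative to raw change scores, by (1 − ρ²) / [2(1 − ρ)] = (1 + ρ)/2. That is 0.75 at ρ = 0.5 and 0.85 at ρ = 0.7. Both correlations are assumed, and the formula ignores the small-sample cost of estimating the slope.

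**The case against.** The strongest reply is that this is a declared decision in a study the protocol calls non-confirmatory. The SAP states what it drops and why. It also cancels the Bayesian primary model, the supportive analyses, the exacerbation analyses and the PK/PD analysis, the last explicitly for low sample size. Keeping one modelled contrast, for the primary endpoint, is a defensible way to close out a terminated trial. This stands, and it limits the point to an improvement.

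Stronger readings that a reader might infer are not supported:
- *All secondary objectives promise a placebo comparison.* Only four of eight do, in the synopsis; in the objectives tables only clearance does. Objectives 7 and 8 (PK, safety) need no contrast.
- *The SAP cancelled a QOL-B model.* There was none. Protocol 12.5.5 planned summaries and the SAP provides them.
- *Fitting CFU proves the other models can be fitted.* It does not. The achieved sample is unknown, each endpoint may have different missing data, HRCT is optional at selected sites, and the SAP carries its own data-permitting caveat.
- *Readers could form no interval at all.* If n and SD per arm are shown, an unadjusted interval for a mean difference can be worked out, as it can from counts for clearance. SAP 6.2.2 does not list its statistics, although SD is standard in 6.1.2 and 7.2. The baseline-adjusted estimate cannot be recovered from summary tables.
- *Regression to the mean distorts these endpoints through selection.* The inclusion criteria set a threshold for sputum load, not for fibrinogen, FEV1 or QOL-B. For those three, only chance imbalance is in play.

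What survives is narrower: the SAP removes the comparison the protocol planned for five endpoints, and termination alone does not account for that when CFU keeps its contrast.

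**Conclusion.** The point holds as a cheap improvement. Protocol 12.5.1 planned between-arm models for five secondary efficacy endpoints; SAP 6.2 cancels them and specifies no difference, odds ratio or interval for any of the six. The cancellation is disclosed, so a reader should not infer a concealed conflict between the documents.

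The size of what goes unshown depends on the achieved number per arm, which the documents do not give. Over an assumed 5 to 20 per arm, the unadjusted 80% half-width is 0.88 to 0.41 SD of change. A gap of half an SD lies inside that margin at 10 per arm (0.59) and just outside it at 15 (0.48). The textual finding does not depend on these assumptions. The primary analysis is not affected.

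**What to change.** In SAP 6.2, replace the blanket cancellation with the following, produced where data allow and labelled as descriptive estimates without tests:

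- **Fibrinogen, FEV1, FVC:** the week-12 QBW251 minus placebo difference with two-sided 80% CI from the SAP 6.1.3 MMRM, using the endpoint's own baseline and baseline-by-visit terms. If the model does not converge, use week-12 ANCOVA on baseline.
- **HRCT airway parameters and month-3 mean daily rescue puffs:** ANCOVA on baseline, with the same output.
- **Clearance:** difference in week-12 proportions with an exact 80% CI. State that this replaces the odds ratio planned in Protocol 12.5.1.1.
- **QOL-B respiratory score:** optional, by the same method as fibrinogen, and labelled as new because the protocol planned only summaries.

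Show n and SD per arm beside each estimate. No new data are needed, and the model code is already required for CFU. The cost is a few extra tables. The intervals will be wide, and the report should say so. As no tests are made, the protocol's position on multiplicity is unchanged.
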